**Table 3. Dose Reduction Table**

Dose Level	Weekly R-roscovitine Dose and schedule
-2	200mg, two times daily x 4 days
-1	200mg, three times daily x 4 days
0	400mg, twice daily x 4 days

- If treatment is delayed for reasons other than toxicity (i.e., unplanned travel or vacation, or lack of transportation to the site) and the subject has insufficient investigational

product available, the subject should resume the usual dosing schedule once drug supply has been made available. However, if the subject has been off therapy for more than 2 weeks, the Investigator will consult the DSMB prior to continuing therapy.

- If a patient permanently discontinues study treatment, the patients will be considered as prematurely discontinued from the study. Patients will have to perform a study phase completion evaluation on the day of the last study drug administration.

### Hepatic adverse events

Hepatobiliary events have been seen in subjects taking seliciclib. As a precaution, the following will be reported as an SAE:

- ALT or AST  $>3 \times$  ULN and total bilirubin  $>2.0 \times$  ULN Other hepatic events should be documented as an AE or an SAE as appropriate.

Liver chemistry stopping and follow up criteria have been designed to assure subject safety and evaluate liver event etiology. All subjects who meet liver chemistry criteria requiring permanent discontinuation of investigational product (IP) must continue to be followed for the study assessments and procedures as defined in **Table 4**.

**Table 4. Liver Chemistry Stopping Criteria**

Hepatic AE	Management/Next Dose for R-roscoxitine

 
• ALT or AST <math>>3 \times</math> ULN and <math><5 \times</math> ULN and total bilirubin <math>\leq 2 \times</math> ULN, without signs or symptoms of hepatitis or hypersensitivity, and who can be monitored weekly
 
	
 
• Hold IP for maximum 2 weeks, repeat liver chemistry testing weekly
 
• Discuss with DSMB for possible re-challenge with IP and define dose reduction
 
• If the treatment is exhibiting efficacy and the subject wants to continue after being informed of the liver chemistry results, then the IP may be re-started at the DSMB defined dose reduction.
 
• Liver chemistries and aforementioned signs and symptoms should be monitored at a minimum of every week until resolution, stabilization, or a return to baseline values, at which point monitoring should be continued per protocol.
 

 
• ALT or AST <math>>8 \times</math> ULN; or
 
• ALT or AST <math>>5 \times</math> ULN persisting for <math>\geq 2</math> weeks; or
 
• ALT or AST <math>>3 \times</math> ULN and (total bilirubin <math>>2.0 \times</math> ULN or INR <math>>1.5</math>); or
 
• ALT or AST <math>>3 \times</math> ULN with signs or symptoms of hepatitis or hypersensitivity*
 
	
 
• Immediately and permanently discontinue IP;
 
• Complete the SAE data collection tool, the liver event CRF, and the liver imaging and/or liver biopsy CRFs, if these tests are performed;
 
• In addition to the liver event follow up assessments defined below, the following are suggested: specialist or hepatology consultation; anti-nuclear antibody, anti-smooth muscle antibody, and Type 1 anti-liver kidney microsomal antibodies; and liver imaging and/or liver biopsy to evaluate liver disease;
 
• Promptly report the event to Cyclacel within 24 hours of learning its occurrence
 
• Monitor every week until liver chemistries resolve, stabilize or return to within baseline values;
 
• Do not re-challenge with investigational product.
 

Hepatic AE	Management/Next Dose for R-roscoxitine
• If ALT or AST>3 and < 5 × ULN for > 4 weeks	Discontinue study drug

\*Includes: worsening of fatigue, nausea, vomiting, right upper quadrant pain or tenderness, fever, rash, or eosinophilia

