## Section 6.0 Treatment of Subjects

Transsphenoidal pituitary tumor resection is the primary therapy for Cushing disease, and yields 30-70% surgical cure rates. Patients with recurrent or residual tumors, and/or are not surgical candidates typically undergo pituitary-directed radiation, adrenalectomy, treated with pasireotide, and/or medical suppression of adrenal gland cortisol production. In this study, we will treat patients with *de novo*, persistent, or recurrent Cushing disease with seliciclib during the period of evaluation and preparation for standard care, which usually takes 4 weeks at our center. We are excluding any subjects who need immediate surgical intervention, i.e. unstable visual field deficit, tumor compression of optic chiasm, or severe metabolic complications. We only will recruit those whom we would recommend for routine evaluation process for standard care. After completion of their participation in the study, subjects will be ready to start standard care. If a given patient responds to the study drug and chooses to stay on the drug after cessation of the trial, clinical data will continue to be collected for further analysis of drug response and monitoring safety.

Study calendar: baseline physical exam, vital signs, weight and laboratory evaluations will be conducted within 7 days prior to the start of therapy. Pituitary imaging and ECG will be performed within 60 days prior to the start of therapy. All procedures and evaluations may be performed within 3 calendar days of that specified in the protocol to accommodate patient convenience and scheduling. Patient informed consent will be obtained prior to any protocol-specific procedures. The schedule of study events is provided in Table 1.

Patients will be administered a dose of oral seliciclib 400 mg twice daily for 4 days every week for total of 4 weeks. Patients will be seen on days 1, 8, 15, 22 and 29 for repeat laboratory testing, assessment of treatment compliance, and toxicity according to National Cancer Institute Common Toxicity Criteria version 3.

The following tests will be performed:

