- Plasma ACTH and serum cortisol levels (every three hours from 9:00 – 15:00)
  - Blood draw will be done via intravenous catheter every 3 hours from 9AM to 3PM.
    - In the case that an intravenous catheter cannot be placed, one blood draw will be performed at every 3 hour interval.

- ECG
- 24 hour urinary free cortisol any time between days 24-28
  - Subjects will collect 3 - 24 hour UFC any time between days 24-28 prior to coming in for study visit 6
- 2 - late night salivary cortisol at 23:00-24:00 between days 24-28

Visit 6: Day #29

- History and physical exam
- Adverse events assessment
- CBC with differential, CMP (including fasting blood glucose), , PT/INR
- Fasting lipid profile, HbA1C
- Hormone profile: PRL, TSH, adjusted T4, free T4, IGF-1, LH, FSH, estradiol for females, testosterone (total and free) for males
- Serum Pregnancy Test (for females of childbearing potential)
- Plasma ACTH and serum cortisol levels (every three hours from 9:00 – 15:00)
  - Blood draw will be done via intravenous catheter every 3 hours from 9AM to 3PM.
    - In the case that an intravenous catheter cannot be placed, one blood draw will be performed at every 3 hour interval.
- ECG
- Visual Fields
- Pituitary MRI
- 24 hour urinary free cortisol on days any time between 30-35
  - Subjects will collect 3 - 24 hour UFC any time between days 30-35 prior to coming in for study completion visit
- 2 - late night salivary cortisol at 23:00-24:00 between days 30-35

Study Completion Visit: Day 36

- History and physical exam
- Adverse events assessment

Table 1. Study procedure flow sheet

Procedures	Screening Visit -60 to -1	Visit 1 Baseline	Visit 2 Day 1	Visit 3 Day 8	Visit 4 Day 15	Visit 5 Day 22	Visit 6 Day 29	Study Completion Visit
Standard of Care Procedures: Items, drugs and services that are part of regular care and would be done even if you did not take part in this research study. These will be billed to you and/or your insurance company.								
Visual Field Exam	X 							
MRI of the Pituitary	X 							
Research Related Procedures: Items, drugs and services done for research purposes only. These will be covered by the sponsor of the study and will NOT be billed to your insurance company.								
Review of medical records	X							
History and Physical Exam	X	X	X	X	X	X	X	X
Serum Pregnancy Test (for female of childbearing potential)	X	X	X	X	X	X	X	X

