### **Liver Chemistry Follow up Criteria**

For all subjects who meet any of the liver chemistry criteria described above, make every attempt to carry out the liver event follow up assessments described below:

- Viral hepatitis serology including:
  - Hepatitis A IgM antibody;
  - Hepatitis B surface antigen and Hepatitis B Core Antibody (IgM);
  - Hepatitis C RNA;
  - Cytomegalovirus IgM antibody;
  - Epstein-Barr viral capsid antigen IgM antibody (or if unavailable, obtain heterophile antibody or monospot testing);
  - Hepatitis E IgM antibody (if subject resides or has traveled outside USA or Canada in past 3 months);
- Serum creatine phosphokinase (CPK) and lactate dehydrogenase (LDH);
- Complete blood count with differential to assess eosinophilia;
- Record the appearance or worsening of clinical symptoms of hepatitis, or hypersensitivity, fatigue, decreased appetite, nausea, vomiting, abdominal pain, jaundice, fever, or rash as relevant on an AE report form;
- Record use of concomitant medications, acetaminophen, herbal remedies, other over the counter medications, or putative hepatotoxins, on the concomitant medications report form;
- Record alcohol use on the liver event alcohol intake case report form.

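### Table 4 lists no action for a new isolated ALT/AST of 5x to 8x ULN, and the general dosing rule that might fill the gap puts conditions before a hold

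*Combined protocol and SAP*

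**What the plan says.** Table 4 has three rows, numbered here from the top.

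- **Row 1** covers ALT or AST above 3x and below 5x ULN with bilirubin no higher than 2x, no hepatitis or hypersensitivity symptoms, and weekly monitoring possible. The action is "Hold IP for maximum 2 weeks, repeat liver chemistry testing weekly", then "Discuss with DSMB for possible re-challenge with IP and define dose reduction".
- **Row 2** covers any of: above 8x; above 5x for two weeks or more; above 3x with bilirubin above 2x or INR above 1.5; above 3x with symptoms. The action is "Immediately and permanently discontinue IP". The footnote defines symptoms broadly: "worsening of fatigue, nausea, vomiting, right upper quadrant pain or tenderness, fever, rash, or eosinophilia".
- **Row 3** stops the drug "If ALT or AST>3 and < 5 × ULN for > 4 weeks".

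The Liver Chemistry Follow up Criteria require a work-up "For all subjects who meet any of the liver chemistry criteria described above".

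The general rules sit outside Table 4. Table 2 holds the drug at Grade 3 for up to 14 days, until recovery to Grade 1 or baseline, then resumes one level lower. Its note directs hepatic events to the liver criteria. Under Dose delays and dose reductions, the opening bullet requires DSMB consultation before a dosing change and exhausted supportive care before a delay or reduction for drug-related toxicity. Later bullets let the investigator hold at Grade 2 or below on judgment, and call for a hold, reduction or withdrawal at attributable Grade 3 or higher. Table 5 orders its adrenal hold directly.

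**The concern.** A liver table should act at least as firmly on a worse value as on a milder one. Here a patient at 4x ULN is held and a comparable patient at 6x has no listed action. The 4x patient also gets the work-up for viral hepatitis and other causes, while the new 6x patient does not meet the condition for it.

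Staff who turn to the general rule find an instruction to consult the DSMB and exhaust supportive care before a delay. Tables 2, 4 and 5 word their holds without either step, and row 1 of Table 4 brings in the DSMB only at re-challenge.

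This is not remote for this drug. Section 8.0 lists hepatic dysfunction among the known common events at this dose. Entry excludes ALT or AST above 1.5x ULN, so 5x is at least 5 / 1.5 = 3.3 times the highest screening value allowed. With only four weeks of treatment, a two-week persistence rule has little time to act.

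**Working it through.** The plan states no figure on this point, so there is none to reproduce. The check applies the table's rules to example values and lays them over the visit and dosing schedule.

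**1. Table 4 applied to an isolated value** (bilirubin no higher than 2x, INR no higher than 1.5, no listed symptom, weekly monitoring possible):

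| ALT or AST, x ULN | New, or 1 week | 2 weeks | 5 weeks |
|---|---|---|---|
| 3.1, 4.9 | row 1 hold | row 1 hold | row 3 stop |
| 5.0 | none | none | none |
| 5.1, 6, 8.0 | none | row 2 stop | row 2 stop |
| 8.1 | row 2 stop | row 2 stop | row 2 stop |

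Exactly 5x is neither below 5x (rows 1 and 3) nor above 5x (row 2). At 6x with any listed symptom, row 2 stops the drug at once, so the gap is confined to patients without symptoms.

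**2. Ceiling on further doses.** Planned doses: 2 per day x 4 days x 4 weeks = 32, in weekly blocks of 8 starting on days 1, 8, 15 and 22. On-treatment chemistry falls on days 8, 15, 22 and 29 (Section 6.0 and Table 1), taking the metabolic panel to include ALT and AST. For a value above 5x and up to 8x:

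| First seen | Two weeks later | Blocks in between | Further doses | Planned doses prevented |
|---|---|---|---|---|
| Day 8 | Day 22 | 2 | 2 x 8 = 16 (50%) | 8 |
| Day 15 | Day 29 | 2 | 2 x 8 = 16 (50%) | 0, dosing is over |
| Day 22 | Day 36 | 1 | 1 x 8 = 8 (25%) | 0, dosing is over |

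In the last case no scheduled test can confirm persistence: the visit headed "Study Completion Visit: Day 36" has no chemistry.

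These counts use nominal days. Section 6.0 adds that "All procedures and evaluations may be performed within 3 calendar days of that specified in the protocol". If visit 3 falls on day 9 and visit 5 on day 22, they are 13 days apart. Without an unscheduled test, confirmation then waits for day 29, and up to 3 x 8 = 24 doses could be given.

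**3. Can the general rules fill the gap?** Whether 5x to 8x is Grade 3 decides whether Table 2 calls for a hold. The documents name the toxicity criteria but give no ALT/AST limits for the grades, so this cannot be settled from them. Table 2's note also leads back to the table that has the gap.

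**4. Number of patients.** The documents give no rate for this band. Assuming a rate p, the expected number is 16p and the chance of at least one is 1 - (1 - p)^16:

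| Assumed p | Expected of 16 | At least one |
|---|---|---|
| 1% | 0.16 | 15% |
| 5% | 0.8 | 56% |
| 10% | 1.6 | 81% |

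**The case against.** The strongest reply is that patients are largely protected elsewhere. Table 2 applies to all patients and holds at Grade 3. The dosing section calls for action on attributable Grade 3 toxicity and lets the investigator hold at lower grades. Section 4.0 allows a 25% reduction at any time for intolerance. The Table 2 note does not say that the Grade 3 row lapses where the liver criteria are silent. This stands, and it limits the point: a reader might infer that the protocol requires dosing to continue at 5x to 8x, and it does not.

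A reader might also infer that every hold is subject to the DSMB and supportive-care conditions. That is too broad. They attach to a delay or reduction for drug-related toxicity, not to permanent stops, and later bullets and tables allow direct holds. What remains is a conflict between a general rule and specific ones, with nothing to say which governs.

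The dose counts stack several assumptions: the value stays in the band, no bilirubin, INR or symptom trigger occurs, and nobody uses the general authority. Several symptoms that trigger the stop, such as nausea, vomiting and fever, are themselves listed as common at this dose. At the weekly tests, a fall below 5x but still above 3x brings the row 1 hold, and a rise above 8x brings a stop. The counts are therefore ceilings, not expected exposure.

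**Conclusion.** The gap in Table 4 is certain from the text: no action for a new isolated value from 5x to 8x ULN until more than 5x has lasted two weeks, and none at any duration for exactly 5x. The conflict between the general preconditions and the direct holds in Tables 2, 4 and 5 is also in the text.

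The consequence for patients is less certain. It depends on ungiven grade limits and on how far investigators use their general authority. At most 16, 16 or 8 of 32 further doses are at stake for a value first seen on day 8, 15 or 22, on nominal days and with no other hold or trigger used. The number of patients is unknown; the 1% to 10% rates are assumptions.

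This should be corrected as a safety-rule defect. It does not touch the sample size or the rule of 3 responders in 16.

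**What to change.** 1. Add a Table 4 row for isolated ALT or AST from 5x to 8x ULN inclusive: hold at once, test weekly and do the follow-up work-up. Allow restart only after recovery to Grade 1 or lower or to baseline, after DSMB discussion and at a reduced dose. State that this restart condition still applies if the value falls back into the row 1 range.
2. In row 2, change the persistence trigger to 5x or higher for two weeks or more, so that exactly 5x is covered.
3. Under Dose delays and dose reductions, state that safety holds under Tables 2, 4 and 5 take effect at once, and that DSMB consultation applies to restart and dose reduction.
4. Add INR no higher than 1.5 to row 1, so that row 2 clearly governs above it.

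With changes 1 and 2, new isolated values from 5.0x to 8.0x give a hold, and the same values at two weeks give a stop. Simply extending row 1 to 8x would be weaker. Its restart depends on apparent efficacy, the patient's wish and the DSMB's dose, with no recovery requirement, and persistent 5x would still have no stop. The investigator, DSMB and drug supplier should confirm whether 5x to 8x needs more than a hold.

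The cost is a short amendment, the work-up for the few patients newly covered (about 0 to 2 on the assumed rates), and possibly unscheduled liver tests after day 29. Section 7.0 accepts up to two weeks of interrupted dosing, so a hold within that limit does not by itself remove a patient from the primary efficacy population; a longer one would.

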### **Liver Chemistry Follow up Criteria**

For all subjects who meet any of the liver chemistry criteria described above, make every attempt to carry out the liver event follow up assessments described below:

- Viral hepatitis serology including:
  - Hepatitis A IgM antibody;
  - Hepatitis B surface antigen and Hepatitis B Core Antibody (IgM);
  - Hepatitis C RNA;
  - Cytomegalovirus IgM antibody;
  - Epstein-Barr viral capsid antigen IgM antibody (or if unavailable, obtain heterophile antibody or monospot testing);
  - Hepatitis E IgM antibody (if subject resides or has traveled outside USA or Canada in past 3 months);
- Serum creatine phosphokinase (CPK) and lactate dehydrogenase (LDH);
- Complete blood count with differential to assess eosinophilia;
- Record the appearance or worsening of clinical symptoms of hepatitis, or hypersensitivity, fatigue, decreased appetite, nausea, vomiting, abdominal pain, jaundice, fever, or rash as relevant on an AE report form;
- Record use of concomitant medications, acetaminophen, herbal remedies, other over the counter medications, or putative hepatotoxins, on the concomitant medications report form;
- Record alcohol use on the liver event alcohol intake case report form.

### **Adrenal adverse events**

If at any time this subject meets any of the adrenal suppression stopping criteria, then proceed as described below.

**Table 5. Adrenal Suppression Stopping Criteria**

Adrenal AE	Management/Next Dose for R-roscoxitine
24 hr UFC < LLN with signs or symptoms of adrenal insufficiency (fatigue, nausea, vomiting, abdominal pain and hypotension)	
 
• Hold IP for maximum 2 weeks
 
• Repeat 24 hr UFC in 1 week
 
• Discuss with DSMB the possibility of re-challenge with IP
 

24 hr UFC <LLN without signs or symptoms of adrenal insufficiency, and who can be monitored weekly	
 
• Continue IP
 
• Monitor weekly until 24 hr UFC stabilize, then monitor 24 hr UFC as per protocol assessment schedule
 

If the subject wants to continue for potential benefit of R-roscoxitine therapy after being informed of the results of 24 hr UFC testing, then the IP may be re-started at the reduced dose agreed upon by the investigator. 24 hr UFC and aforementioned signs and symptoms

should be monitored at a minimum of every week until resolution, stabilization, or a return to baseline values, at which point monitoring should be continued per protocol.

### **Glucose metabolism adverse events**

The principal investigator is to evaluate the risks for hyperglycemia in all patients, following established guidelines by the American Diabetes Association (ADA) and European Association for the Study of Diabetes (EASD). The principal investigator is to educate the patient on the signs and symptoms of hyperglycemia.

Patients with a prior history or new diagnosis of impaired fasting glucose, impaired glucose tolerance or diabetes mellitus, or at risk of developing these conditions should monitor their blood glucose by fingerstick twice daily (fasting and 2-hours post-prandial). The patients will be encouraged to keep a diary for their blood glucose for appropriate management of the disease throughout the trial and present the collected data to their physician/diabetes specialist for evaluation.

Any patient showing a fasting plasma glucose  $> 130$  mg/dL (7.2 mmol/L), or 2-hour post-prandial capillary glucose (PPG)  $\geq 180$  mg/dL (10 mmol/L) on two consecutive measurements that are approximately 14 days apart, and/or HbA1c  $> 7\%$  is evaluated by a diabetes specialist for appropriate treatment. In addition, these patients are given information regarding diabetes disease management. Initiation or adjustment of hypoglycemic treatment is considered as early as possible at the discretion of the diabetes specialist. The above instructions regarding glucose monitoring by fingerstick and collection of blood level in a diary are given to the patients.

Patients who develop symptoms of diabetes mellitus out of control and/or fasting blood glucose values consistently as high as or above 240 mg/dL in spite of appropriate therapeutic interventions are discontinued from the study, as are those patients whose HbA1c is greater than or equal to 8% in spite of appropriate therapeutic intervention.

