### Screening visit: Day -60 to -1

- History and physical exam
- Dexamethasone dispensed
  - Dexamethasone will be dispensed during the screening visit. Study doctor will explain when the subject should take it. During an overnight dexamethasone suppression test, 8mg of dexamethasone will be taken orally the night before at 11:00 PM. Subjects will go to the local Quest laboratory the next morning and will have their blood drawn between 8:00 AM - 9:00 AM to test their serum cortisol levels. Dexamethasone, which acts like a cortisol, decreases the amount of ACTH released by the pituitary gland, which then decreases the amount of cortisol released by the adrenal glands. More than 50% suppression of morning cortisol level after dexamethasone administration will confirm the diagnosis of Cushing's disease. Patients who had previously undergone dexamethasone suppression test at Cedars-Sinai Medical Center or if the patient has been confirmed with diagnosis such as a previous surgery or IPSS a repeat exam is not required.
- 24 hour urinary free cortisol x 2
  - Subjects will be given 2 containers to collect 2 - 24 hour UFC
  - The 2 - 24 hour UFC can be collected anytime between one week after taking dexamethasone and the baseline visit
  - Subjects will drop off the 2 - 24 hour UFC at their local Quest laboratory

- ECG
- Visual fields
- Pituitary MRI
- HbA1C
- CBC with differential, CMP (including fasting blood glucose), LFTs
- Hormone profile: PRL, TSH, thyroid panel, free T4, IGF-1, LH, FSH, estradiol for females, testosterone (total and free) for males
- PT/INR
- Serum Pregnancy Test (for females of childbearing potential)
- Serum cortisol level at 8:00-9:00 AM on the day of screening visit, then at 8:00-9:00 AM the next day after an overnight 8 mg dexamethasone

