#### Baseline visit 1: Day -7

- CBC with differential, CMP (including fasting blood glucose), PT/INR
- Fasting lipid profile, HbA1C, Hormone profile: PRL, TSH, adjusted T4, free T4, IGF-1, LH, FSH, estradiol for females, testosterone (total and free) for males,
- Plasma ACTH and serum cortisol levels (every three hours from 9:00 – 15:00)
  - Blood draws will be done via intravenous catheter every 3 hours from 9AM to 3PM.
    - In the case that an intravenous catheter cannot be placed, one blood draw will be performed at every 3 hour interval.
- Serum Pregnancy Test (for females of childbearing potential)
- ECG
- Visual fields
  - 2 x late night salivary cortisol collection at 23:00-24:00 PM on any nights between baseline visit 1 and visit 2. The subject will rinse their mouth thoroughly with water and discard (do not swallow). The subject will hold the Salivette(R) at the rim of the suspended insert and remove the stopper and remove the swab. The swab will be placed under the tongue until well saturated (approximately one minute). The subject will then return the saturated swab to the suspended insert and close the Salivette(R) firmly with the stopper.
- 24 hour urinary free cortisol x 3
  - Subjects will be given 3 containers to collect 3 - 24 hour UFC
  - The 3 - 24 hour UFC can be collected anytime between the baseline visit 1 and visit 2.
  - Subjects will drop off the 3 - 24 hour UFC at their local Quest laboratory

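### The two-week repeat in the glucose referral rule does not fit daily fingersticks and, if it also covers fasting glucose, does not fit the weekly on-treatment labs; a minor safety-rule correction

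*Combined protocol and SAP*

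**What the plan says.** The rule is in Section 8.0, Glucose metabolism adverse events. Specialist evaluation follows from any of three limbs:

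- fasting plasma glucose above 130 mg/dL;
- 2-hour post-prandial capillary glucose of 180 mg/dL or more;
- HbA1c above 7%.

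The words "on two consecutive measurements that are approximately 14 days apart" come after the post-prandial limb. The text does not say whether they also govern the fasting limb. The same paragraph gives the purpose of referral: "Initiation or adjustment of hypoglycemic treatment is considered as early as possible at the discretion of the diabetes specialist".

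The measurements that feed the rule are these:

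- **Fingersticks.** Patients with known, newly found or possible future dysglycemia "should monitor their blood glucose by fingerstick twice daily (fasting and 2-hours post-prandial").
- **Laboratory fasting glucose.** Section 6.0 lists it at screening ("CBC with differential, CMP (including fasting blood glucose), LFTs") and at Baseline visit 1 ("CBC with differential, CMP (including fasting blood glucose), PT/INR"), then at Days 8, 15, 22 and 29. Neither Visit 2 (Day 1) nor the last visit ("Study Completion Visit: Day 36") lists a metabolic panel, and Table 1 agrees.
- **HbA1c.** It is taken at screening and baseline, and next at Visit 6, Day 29 ("Fasting lipid profile, HbA1C").

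**The concern.** A numeric safety trigger should be one that the scheduled measurements can satisfy. This one asks for two successive readings two weeks apart, in a trial that reads laboratory glucose weekly and fingersticks daily over a 4-week treatment period. Site staff who apply it literally would have no qualifying post-prandial pair. If they take the repeat to cover both glucose limbs, they would nominally have no qualifying fasting pair among the on-treatment visits either.

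The parsing changes what happens to a patient. Take someone with normal glucose at baseline and a fasting value above 130 mg/dL from Day 8. If the repeat belongs to the post-prandial limb only, that patient is referred at Day 8. If it covers both limbs, the glucose trigger is not nominally met during the scheduled visits. At stake is the timing of referral for glucose that first rises on treatment, in a disease that Section 2.0 says predisposes to diabetes. The efficacy conclusion is not at stake.

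**Working it through.** **Inputs.** Required gap: about 14 days between consecutive values (Section 8.0). Scheduled fasting glucose: screening, Day -7, and Days 8, 15, 22 and 29 (Section 6.0, Table 1). Visit window: 3 calendar days; baseline labs within 7 days before the start of therapy (Section 6.0, study calendar). Fingersticks: two a day, one of them post-prandial (Section 8.0).

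**Post-prandial limb.** No visit schedules a post-prandial test, so the values come from fingersticks.

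- With one post-prandial value a day, the gap between consecutive values is about 1 day, against the 14 required.
- Two values 14 days apart have 14 - 1 = 13 daily values between them, so they are not consecutive.
- If any two high values two weeks apart were accepted, the earliest referral would be 14 days after the first, which is half of the 4 x 7 = 28 days of treatment.

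This misfit does not depend on how the sentence is parsed.

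**Fasting limb, if the repeat governs it too.** Gap = later day - earlier day:

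| Adjacent pair | Nominal gap (days) | About 14? |
|---|---|---|
| Day -7 / Day 8 | 14 (no Day 0), or 15 if a Day 0 is counted | yes |
| Day 8 / Day 15 | 15 - 8 = 7 | no |
| Day 15 / Day 22 | 22 - 15 = 7 | no |
| Day 22 / Day 29 | 29 - 22 = 7 | no |

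So 0 of 3 adjacent on-treatment pairs nominally qualify. Four details bound that result:

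- *Visit windows.* Moving both visits by 3 days in opposite directions gives 7 - 6 = 1 to 7 + 6 = 13 days. A 13-day gap could pass as about 14, so the statement holds for the nominal schedule only.
- *Non-adjacent labs.* Days 8/22 and 15/29 are 14 days apart, but each pair has a scheduled value between its two members.
- *Baseline/Day 8.* This pair qualifies only if glucose was already high before dosing. Baseline labs may be drawn from Day -7 to Day -1, so with no Day 0 the gap runs from 14 down to 8 days.
- *Screening/baseline.* This pair can also be two weeks apart (for example Day -21 and Day -7, 14 days), again only for glucose that is high before treatment.

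**Fasting limb, if the repeat governs the post-prandial limb only.** One fasting value above 130 mg/dL at Day 8, 15, 22 or 29 triggers referral at once, and there is no misfit on this limb.

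**Whether HbA1c fills the gap.** HbA1c above 7% can act at screening or baseline. After that it is next measured on Day 29, so it gives no scheduled on-treatment trigger before then.

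**The case against.** The strongest reply is grammatical. The fasting limb is set off by a comma before the post-prandial limb, and the repeat phrase follows the latter, so the more natural reading attaches the repeat to post-prandial values alone. A single fasting value from any weekly panel then triggers referral without delay. This stands, and it means that the fasting-pair count above is conditional. It does not rescue the post-prandial limb, and the text does not settle the parsing.

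Second, the trigger is not the only path to a specialist. Patients with or at risk of dysglycemia are encouraged to keep a glucose diary and show it to their physician or diabetes specialist, with no two-week condition. In this disease, being at risk could cover most patients. The principal investigator evaluates hyperglycemia risk in everyone, chemistry is reviewed weekly, and nothing bars earlier referral. The general dose rules (Section 8.0, Table 2) also apply: hold at Grade 3, discontinue at Grade 4, and investigator discretion below that. Clinically significant abnormal labs are recorded as adverse events when they meet the definition. All of this stands. The dose and recording rules do not themselves produce a referral, but together these provisions limit the harm.

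A reader might infer three stronger things that the documents do not support:

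- *That new hyperglycemia on treatment goes unmanaged.* The routes just listed exist, and the stop for symptoms or for fasting glucose consistently at 240 mg/dL or above remains.
- *That this is a seliciclib toxicity signal left unwatched.* Neither list of known adverse effects (Sections 5.0 and 8.0) includes hyperglycemia.
- *That the HbA1c limits contradict each other*, because entry excludes diabetic patients above 8% while the stop applies when HbA1c "is greater than or equal to 8% in spite of appropriate therapeutic intervention". The stop depends on treatment having been tried, so a patient who enters at exactly 8.0% is not stopped automatically. The two limits serve different purposes.

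**Conclusion.** The point holds as a minor correction to a safety rule. The post-prandial limb misfits the schedule on either reading: about 1 day between values against about 14 required. The fasting limb misfits only if the repeat governs it too. In that case 0 of 3 adjacent on-treatment pairs nominally qualify, and baseline/Day 8 qualifies only for glucose that was already high.

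This assumes the nominal visit days, no dose delay, and a literal meaning of consecutive. The documents give no on-study glucose or HbA1c distribution, so the number of patients whose referral would be delayed cannot be estimated, and no claim is made that it is large. The primary endpoint, the error rates and the 3-of-16 decision rule are untouched.

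**What to change.** In Section 8.0, Glucose metabolism adverse events, delete the 14-day interval and state each limb separately:

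- **Fasting.** A single scheduled fasting plasma glucose above 130 mg/dL triggers specialist evaluation. If the investigators intend confirmation, require a repeat no later than the next weekly visit.
- **Post-prandial.** A fingerstick value of 180 mg/dL or more triggers evaluation once a second value within about a week confirms it.
- **HbA1c.** Leave the limb and the existing stops as they are.

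The thresholds stay with the investigators. The single-value option needs only a change of wording, because the weekly panels and fingersticks are already planned. Its cost is a few more specialist referrals. The confirmation option puts referral up to 7 days later than a single-value rule. It also needs a decision for a first high value on Day 29, since the Day 36 visit has no metabolic panel: either count the single value or add a repeat there. For that reason the single-value rule is the simpler choice.
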